10.1 Pretreatment Evaluations/Management

- Complete history and physical examination with a detailed neurological examination within 15 days of study registration.
- Quality of Life form FACT-Br completion (see Appendix F)
- Neurocognitive assessment: HVLt, TMT, MMSE (see Appendices D and E)

10.2 Screening Examination

Patients will be registered only after eligibility criteria are met. Once research staff and PI have verified that the patient is eligible per Departmental policy and that the study ongoing regulatory requirements have been met, a patient-specific case number will be assigned. An informed consent must be signed by the patient before any screening procedure takes place. If, however,

standard of care evaluation procedures have been obtained and are within the screening evaluation time points, the SOC procedures do not need to be repeated and may be included in the screening examination. All of the eligibility inclusion and exclusion criteria should be satisfied during each screening process.

10.3 Treatment Period

Treatment will range from 1 to 5 consecutive business days and those patients that get multiple treatments will be observed every day by radiation therapists.

Those patients that will be treated in 5 days are the following:

- 1) at least 1 metastasis > 3cm
- 2) V12 > 20 cc for normal brain parenchyma, all lesions will receive 5 Gy x 5
- 3) If there is a brainstem lesion

If a treatment interruption occurs but the patient completes all five treatments within 10 business days, then this would not be considered a protocol deviation.

Sexually active, subjects must agree to use appropriate contraceptive measures for the duration of the study treatment (i.e. from SRS CT simulation to the completion of SRS treatment, which is approximately 1-2 weeks).

10.4 End of Treatment

They will be seen by either an NP or MD to be given discharge instructions. Any acute side effects of treatment will be assessed via CTCAE v.4 and documented.

10.5 Follow-up Period

Follow-up period will be two years. The first visit is approximately 4 weeks post SRS, every 3 months in the 1st year post SRS, and then every 6 months in the 2nd year within \pm 2-weeks. Each visit will include an updated medical history and physical exam, neurological exam, performance status, adverse events and toxicity assessment, quality of life, and neurocognitive testing. During the follow up period a standard of care contrasted MRI and/or tumor measurements will be performed as clinically indicated by the treating investigator.

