The primary endpoint will be the proportion of patients who live longer than predicted based on the diagnosis-specific GPA score. The Kaplan-Meier estimator will be used to describe the survival of all patients treated with SIMT SRS. Secondary endpoints will be the rate of recurrence at the treated metastases sites, the rate of new brain metastases at a site different from the SRS-treated metastases sites, the rate of death due to neurological causes, and the prevalence of significant adverse events. Exploratory endpoints include change over time in neurocognition and quality of life, quantification of dosimetric measures, the rate of salvage therapy, the rate of radionecrosis at the SRS treatment sites, and the rate and intensity of steroid-usage post-SRS. Dosimetric endpoints to be collected include: maximum and minimum dose to GTV, and conformity index. These endpoints will be compared to historical data calculated by Sperduto et al. from the literature on radiosurgery alone, radiosurgery plus WBRT or WBRT alone, where appropriate.¹⁶ All patients will be evaluated for neurocognitive function via MMSE, HVL, and Trail-making tests A & B, quality of life via FACT-Br, and for local recurrence via MRI every 3 months over the course of the study. These evaluations will be done at regular follow-up evaluations or when local recurrence is suspected on the basis of symptoms. Distant recurrence is defined as the appearance of new brain metastases at a site different from that of the original metastases. Recurrence will further be defined as a new area of enhancement that measures greater than 5 millimeters in the axial plane on MRI. The length of time to recurrence of the original brain metastases will be calculated from the date of the brain metastases radiosurgery to the date that a recurrence was detected by MRI. Patients with suspected recurrent tumor and/or who are symptomatic may undergo a stereotactic biopsy to evaluate for radionecrosis versus recurrent brain metastases, as is standard of care.

There may or may not be a direct medical benefit to participants. The hope is that but the information gained from this study will help in treating patients with brain metastases in the future.

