10 PATIENT ASSESSMENTS

A clinical research nurse will contact each patient by telephone within 2 weeks after the SRS procedure to inquire as to the patient's health status if the patient does not have an appointment with an oncologist at DUMC within that time.

At follow-up visits patients will be evaluated as described in the Table below. Patients will be seen in clinic and undergo repeat MRI imaging as standard of care every 3 months for the first 12 months following completion of SRS and every 6 months for the following 12 months. During the follow up visits, the patient will be examined for new or recurrent neurologic signs/symptoms. On MRI, local recurrence is defined as the reappearance of a metastasis in the SRS treated field (within the 50% isodose line). Each treated lesion will be documented separately. Distant recurrence is defined as the appearance of a new brain metastasis outside the SRS field (completely outside the 50% isodose line). To be deemed a recurrence or new lesion, the lesion must measure at least 5 mm in the axial plane on MRI.

Patients with a recurrent or new lesion, who are symptomatic, may undergo a biopsy to determine if the lesion is secondary to radionecrosis or metastasis. Appropriate salvage therapy will be performed at the discretion of the treating radiation oncologist.

If on evaluation the treating physician decides not to pursue an MRI because of clinical decline, this will not be a protocol violation. The most current brain MRI will be used in the determination of local control. Conversely, if a brain MRI needs to be done at an earlier time point due to medical necessity, an MRI at that time point will also not be a protocol deviation and can be included in the data collection. Brain MRI's may be done at 3 month intervals with a one month before or after allowance.

In addition, included in the category of updated medical history is pertinent interim oncologic and medication history. A medical oncologist overseeing patient's standard of care will have been responsible for chemotherapy management as well as systemic staging scans. We will record the type and duration of systemic therapies with each visit as well as the latest information on staging scans (stable or regression vs. progression of disease).

Study Calendar

	Pre-study	During SRS	First visit post SRS (\approx 4 wks.)	Follow-up Yr.1: every 3-mos. Yr. 2: every 6-mos. (\pm 2 wks.)
Informed Consent	X			

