PE including Neurological exam, updated Med History.	X ¹		X	X
Neurocognitive Assessments	X		X ⁴	X ⁴
Performance Status	X		X	X
FACT-Br	X		X	X
Adverse Event Assessment	X	X	X ³	X ²
MRI	X			X ²
Tumor Measurements	X			X ²

1. No more than 15 days prior to SRS.
2. As clinically indicated
3. Acute toxicity will be collected at this visit which will occur approximately 4 weeks' after the last fraction of SRS. If patients are unable to attend follow up due to clinical decline this would not be considered a protocol deviation.
4. It will not be considered a protocol deviation if a patient declines to complete neurocognitive testing at any follow up visit.

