10.7.2 Follow-up Requirements for Early Withdrawal

Patients will continue to be assessed every three months with an MRI and history and physical exam which is our standard of care.

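### Follow-up MRI is on a fixed schedule in some sections and left to clinical indication in others, while recurrence is censored at last follow-up; one-year recurrence would tend to be understated

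*Combined protocol and SAP*

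**What the plan says.** **Passages that give a schedule.** Section 3.3 has all patients evaluated "for local recurrence via MRI every 3 months over the course of the study". Section 3.5 says local control and distant failure are collected at 3, 6, 9 and 12 months. Section 10 has patients "undergo repeat MRI imaging as standard of care every 3 months for the first 12 months following completion of SRS"; for the second year it lengthens the interval to 6 months. Section 10.7.2, on early withdrawal, says: "Patients will continue to be assessed every three months with an MRI and history and physical exam which is our standard of care".

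**Passages that leave imaging open.** Section 10.5 fixes the visits and lists what each one includes. MRI is not on that list; a separate sentence says that standard-of-care contrasted "MRI and/or tumor measurements will be performed as clinically indicated by the treating investigator". In the Study Calendar, the follow-up entries for MRI and for tumor measurements carry footnote 2, which reads "As clinically indicated".

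**Passages that loosen the schedule.** Section 3.3 adds: "These evaluations will be done at regular follow-up evaluations or when local recurrence is suspected on the basis of symptoms". Section 10 states the window permissively: "Brain MRI's may be done at 3 month intervals with a one month before or after allowance". It also accepts a scan omitted for clinical decline, or done early for medical necessity, without a protocol deviation or violation.

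**How recurrence is counted.** Section 3.3 dates recurrence of the treated metastases at MRI detection. Section 10 requires any recurrent or new lesion to measure at least 5 mm on MRI. Sections 13.5.1 and 13.5.2 use Kaplan-Meier estimates with a one-year figure. They censor patients without recurrence at last follow-up if alive and at death otherwise.

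**The concern.** Local recurrence is the key secondary endpoint and distant recurrence is another secondary endpoint. Without a scan neither can be recorded, so the imaging rule decides when, and whether, an event enters the analysis. If imaging follows clinical indication, recurrences without symptoms are found late or not at all. A patient who attends clinic without a scan still adds recurrence-free time, because the censoring date is last follow-up and not the last scan.

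The protocol gives these results weight. Sections 3.6 and 13.4.1 say local control is of primary interest and that survival was made primary because recurrence is hard to confirm without biopsy. Section 13.4.3 names local control among the factors in deciding on further use of the technique. Section 10.7.1 ends neurocognitive testing once progression in the brain is shown, so scan timing also affects who contributes to a key exploratory endpoint.

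**Working it through.** The plan states no figure that depends on this point, so there is none to reproduce. The check is a comparison of the passages, followed by a purely illustrative calculation.

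**1. The passages side by side**

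| Section | Year 1 | Year 2 | Window |
|---|---|---|---|
| 3.3 | MRI every 3 months, or on suspicion | every 3 months (whole study) | not stated |
| 3.5 | local control and distant failure at 3, 6, 9, 12 months | not stated | not stated |
| 10, text | MRI every 3 months | every 6 months | MRI: one month either side |
| 10.7.2 (after withdrawal) | MRI every three months | no end stated | not stated |
| 10.5 | MRI as clinically indicated | as clinically indicated | visits: 2 weeks either side |
| Study Calendar | MRI as clinically indicated, in a column headed by the visit schedule | same | visits: 2 weeks either side |

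Three mismatches follow:
- In year 1, a fixed interval stands against clinical indication.
- In year 2, Section 3.3 (every 3 months) differs from Section 10 (every 6 months), and both differ from 10.5.
- The MRI window of one month differs from the visit window of 2 weeks.

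The one-year estimates depend mainly on the first.

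**2. A test case.** A well patient attends the 6-month visit and has no scan. Under 10.5 and calendar footnote 2 this complies. Under 3.3 and the Section 10 schedule it does not, and the clinical-decline allowance does not cover it. The two sets of passages therefore give different answers for the same patient.

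**3. Direction of the effect.** Suppose that patient has a silent recurrence at month 5, is seen at months 6, 9 and 12 without a scan, and is last seen at month 12. Under 13.5.1 the patient is censored at month 12 and stays in the recurrence-free risk set throughout. Censoring at the last MRI would remove the unscanned months. An unseen event together with retained time at risk pushes the one-year recurrence estimate down.

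**4. Illustration, with every input assumed.** Let recurrence times be exponential with true one-year recurrence p, so the monthly rate is λ = −ln(1 − p)/12. Let a share s of recurrences ever prompt a scan, with an exponential lag of mean 3 months (μ = 1/3). Unscanned patients are kept at risk as under 13.5.1. The observed one-year figure is then

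s × {1 − [μ·exp(−12λ) − λ·exp(−12μ)]/(μ − λ)}.

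- p = 17%: λ = 0.01553 and the bracketed factor is 0.130. The result is 6.5%, 9.8% and 13.0% for s = 50%, 75% and 100%.
- p = 30%: λ = 0.02972 and the factor is 0.233. The result is 11.7%, 17.5% and 23.3%.

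A simulation of 40,000 patients per setting, with independent death at median survival of 6, 9 or 15 months, agreed. It gave about 7%, 10% and 13% for p = 17%, and 11–12%, 17–18% and 23–24% for p = 30%. Scheduled 3-monthly scanning in the same simulation gave about 17% and 29–31%.

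The 17% is the complement of the 83% one-year control quoted in Section 4.2, from 26 patients with a median follow-up of 3.3 months. The 30%, the shares, the lag and the survival medians have no source in the documents. These numbers show direction only.

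**The case against.** The best defence is a harmonised reading. The sentence in 10.5 refers to standard-of-care MRI, and Sections 10 and 10.7.2 describe that standard as 3-monthly. Section 3.5 points the same way. Clinical indication could then be shorthand for the flexibility Section 10 already allows. The calendar is also weak evidence: the same footnote sits on follow-up adverse event assessment, which 10.5 and Section 11 require at every visit, so it seems to be used loosely.

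Much of this stands. The weight of the text favours 3-monthly assessment in year 1, and practice may follow it. It does not remove the conflict, because 10.5 sets out the visit content, omits MRI from it and makes the scan conditional on the investigator's judgement. The harmonised reading also leaves the year-2 difference untouched.

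Other points for the defence also stand. Per-lesion recording at every MRI is already required by Sections 9.3 and 10, so it is not missing. The affected endpoints are descriptive, with no test or threshold. Censoring at the last MRI would be worth stating under any imaging rule; the inconsistency makes it matter more.

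A reader might infer that the trial will scan only on symptoms, or that its recurrence estimates are biased by a known amount. The documents support neither: they do not say which passage governs, and they give no rate at which recurrences prompt a scan.

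**Conclusion.** The inconsistency is real and should be corrected. As written, a skipped routine scan in a well patient complies with 10.5 and the calendar but not with 3.3 and Section 10. Because recurrence needs an MRI and censoring is at last follow-up, unscanned time is counted as recurrence-free, and the one-year local and distant recurrence estimates would tend to be too low. This rests on two conditions: that some routine scans are omitted in patients who are still seen, and that some recurrences in them are silent. If 3-monthly scanning is in fact followed, the effect is small.

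The size cannot be derived from the documents. It would be wrong to extend the point to the primary endpoint: survival against the GPA expectation does not depend on MRI timing.

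**What to change.** Reconcile Sections 3.3, 3.5, 10, 10.5, 10.7.2 and the Study Calendar so that endpoint imaging and the associated tumor measurements follow one schedule, covering both years and with one stated window, set in advance for all patients. The choice of interval is for the investigators. Treat clinically indicated scans as additional to that schedule, and keep the existing allowance for clinical decline.

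In Sections 13.5.1 and 13.5.2, censor time to local and distant recurrence at the last evaluable MRI and not at last follow-up. State how the time between the last MRI and death is handled for patients who die without a detected recurrence. Report the number of scans done and missed at each time point.

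The cost is an amendment to wording and one censoring rule. No additional imaging is implied if 3-monthly MRI is already standard of care, as the protocol says. The downsides are that some scans missed outside the allowance become deviations, and that follow-up time for recurrence is slightly shorter.

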10.6 End of Study

End of study will be completion of data analysis.

10.7 Early Withdrawal of Subject(s)

10.7.1 Criteria for Early Withdrawal

Subjects may voluntarily withdraw from the study at any time. The PI may also withdraw a subject from the study at any time based on his/her discretion. Reasons for PI-initiated withdrawal may include, but is not limited to the following:

- Protocol deviation
- Administrative issues
- Local or distant recurrence evident on Brain MRI imaging

Patients who demonstrate local or distant progression in the brain after study treatment will be followed for overall survival only but will not have neurocognitive testing performed.

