To summarize, lesions will be treated in one fraction unless a lesion is greater than 3cm, located in the brainstem, or the V12 of the normal brain exceeds 20 cc.

In the setting of multiple metastases, a lesion(s) may need to be resected because of large size or mass effect that causes serious neurologic deficits. The resulting resection cavity/cavities can be treated along with the other unresected metastases with the SIMT technique. This has not occurred commonly in our practice but surgery does not preclude the use of this technology.

Isodose distributions must be calculated, and the prescription isodose line clearly designated, for each target lesion in the transverse, coronal, and sagittal planes. The isodose distributions on the required three planes for each target lesion will include isodose lines (in % dose) that represent 20% dose increments. Cumulative dose-volume histograms must be calculated for all target lesions, as well as the brainstem, optic chiasm, optic nerves, eyes and normal brain parenchyma.

Each lesion will be consistently labeled according to institutional protocol and separately followed and documented. With every MRI, any changes in each lesion will be recorded. MRI image registration using department radiation planning software (iPlan) will aid in detecting differences in lesion size and number.

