13.5.1 Key Secondary Objective

The time until local brain recurrence will be calculated as the time between initiation of SIMT SRS and local recurrence of brain metastases. The time to local brain recurrence will be censored at the time of last follow-up if the patient remains alive without local recurrence, or will be censored at death if the patient dies without local recurrence of brain metastases. A Kaplan-Meier estimator will be used to describe the time until local recurrence. Within the context of Kaplan-Meier curve, an estimate of the proportion of patients without local brain recurrence one year after SIMT SRS treatment will be generated. The time until local brain recurrence will also be described within diagnosis-specific subgroups.

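### Sections 10.7.1 and 10.7.2 give different follow-up after brain progression; if 10.7.1 governs, the death-censored Kaplan-Meier recurrence estimates of Section 13.5 are too low

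*Combined protocol and SAP*

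**What the plan says.** Section 10.7.1 lists among the possible reasons for withdrawal by the investigator "Local or distant recurrence evident on Brain MRI imaging". It then says of patients with local or distant progression in the brain that they "will be followed for overall survival only but will not have neurocognitive testing performed".

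Section 10.7.2, on follow-up after early withdrawal, says: "Patients will continue to be assessed every three months with an MRI and history and physical exam". It calls this standard of care. Section 9.3 adds: "With every MRI, any changes in each lesion will be recorded".

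Section 13.5.1 (key secondary objective) defines time to local recurrence, which "will be censored at the time of last follow-up if the patient remains alive without local recurrence", and which is otherwise censored at death. Section 13.5.2 uses the same rule for distant recurrence. Neither endpoint is censored at the other type of failure or at the last scan, and the date of last follow-up is not defined. Section 10 says "The most current brain MRI will be used in the determination of local control", but does not make that MRI the censoring date.

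**The concern.** A patient withdrawn for brain recurrence falls under both rules. A patient who progresses and is not withdrawn falls only under 10.7.1, so on a literal reading the withdrawn patient is followed more closely than the one still on study. No section settles this or says whether MRIs after progression count for the recurrence endpoints.

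Under 10.7.1, a patient with a distant failure has no further study imaging. Section 13.5.1 nevertheless keeps that patient in the risk set for local recurrence until last contact or death. The patient adds to the denominator but cannot have an observed event, so the Kaplan-Meier recurrence estimate is pulled down. The same happens to distant recurrence after a local failure.

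Local recurrence is the key secondary endpoint, and Section 13.4.3 names local control among the factors for deciding on further use of the technique. Each patient's first brain failure is still seen, and survival is followed under either rule.

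**Working it through.** The plan gives no design figure for recurrence, so there is none to reproduce. The size below is an illustration.

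**Inputs**
- One-year local control 83% (Section 4.2) and six-month survival 60% (Section 3.2), both from one earlier study of 26 patients. The 83% is treated as per patient, which the protocol does not state.
- One-year distant failure: not in the documents; assumed 30% and 60%.
- Constant, independent hazards; 40 patients; scans at 3, 6, 9 and 12 months. A failure is detected at the next scan if the patient is alive.

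**Monthly hazards**
- Local: a = -ln(0.83)/12 = 0.01553
- Death: m = -ln(0.60)/6 = 0.08514
- Distant: b = -ln(0.70)/12 = 0.02972, or -ln(0.40)/12 = 0.07636

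**All patients imaged throughout.** The one-year estimate is the sum over scans k = 1 to 4 of exp(-3(k-1)a) × (1 - exp(-3a)). With 1 - exp(-3a) = 0.0455, this is 0.0455 × (1 + 0.954 + 0.911 + 0.870) = 17.0%.

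**10.7.1 with 13.5.1 as written.** Only patients with no distant failure at an earlier scan can show a local event, but all survivors without an observed local event stay at risk. Independent death drops out of the Kaplan-Meier estimate. With q = exp(-3(a+b)), it becomes 0.0455 × (1 + q + q² + q³):
- 30% distant failure: q = 0.873, sum 3.301, estimate **15.0%** (2.0 points low)
- 60% distant failure: q = 0.759, sum 2.773, estimate **12.6%** (4.4 points low)

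**Distant recurrence.** Replacing 1 - exp(-3a) by 1 - exp(-3b) gives 28.2% against 30%, and 56.8% against 60%.

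**Counts out of 40 in year 1.** Scan-detected local recurrences with full imaging are 40 × Σ exp(-3km) × exp(-3(k-1)a) × (1 - exp(-3a)) = 3.79. With the extra factor exp(-3(k-1)b), 3.45 or 3.01 are seen, so about 0.3 to 0.8 are missed. Patients with any brain progression detected by month 12 number 9.6 or 16.0.

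**Sensitivity of the one-year local estimate**

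| Setting | Full imaging | 30% distant | 60% distant |
|---|---|---|---|
| Base case | 17.0% | 15.0% | 12.6% |
| Continuous detection: a/(a+b) × (1 - exp(-12(a+b))) | 17.0% | 14.4% | 11.3% |
| Local control 90% | 10% | 8.8% | 7.4% |
| Local control 70% | 30% | 26.6% | 22.5% |
| Shared gamma frailty, variance 1 (simulated) | about 17% | 13.6% | 9.7% |

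**Does changing the censoring date suffice?** With independent failures, simulation with censoring at the last brain MRI returns 17.0%. With the shared frailty and continuous detection, stopping observation at the other failure and censoring there reads 14.6%, 12.5% and 9.8% for distant failure of 30%, 50% and 70%, against 17%. The censoring date alone is therefore not enough when the failures are positively associated.

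**Sampling error.** The standard error of the one-year local estimate with 40 patients and full imaging is about 8.6 points (20,000 simulated trials).

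**Against the Section 5 wording.** Section 5 describes the endpoint as the share of patients with a local recurrence in the first year. On the same inputs that crude share is 3.79/40 = 9.5% by scan. In continuous time it is a/(a+m) × (1 - exp(-12(a+m))) = 10.8%.

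**The case against.** The strongest reply is that the sections can be read together without loss. Section 10.7.2 is the provision on follow-up after withdrawal. The sentence in 10.7.1 names only neurocognitive testing as dropped, Section 9.3 records lesion changes at every MRI, and the salvage endpoint in 13.6.2 exists only after failure. This stands as a plausible reading. If it is the intended one and the results are recorded, imaging continues and the bias largely disappears. It does not remove the words in 10.7.1 that limit follow-up to survival, or the patients who progress without being withdrawn.

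A reader might infer that local control will look better than it is, without qualification. The documents do not support that. Because 13.5.1 censors at death, even the lowered 15.0% to 12.6% lies above the crude share of 9.5% to 10.8% that matches Section 5. The downward direction holds only against the death-censored estimate.

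A reader might also infer that salvage is not collected. That is not established: Section 10 includes interim oncologic and medication history, the list in 10.8.1 is not exhaustive, and the case report form is not in the documents.

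Section 10.7.2's three-monthly MRI also differs from Section 10, which gives MRI "every 3 months for the first 12 months following completion of SRS and every 6 months for the following 12 months". That concerns year 2 and does not affect the one-year figures.

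Finally, the model holds the local hazard constant after distant failure, whereas salvage could change it. That limits how precisely the size can be stated.

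**Conclusion.** The two follow-up rules conflict as written, and the choice between them changes a key secondary estimate. If 10.7.1 governs and 13.5 is applied literally, the death-censored one-year local recurrence reads about 2.0 to 4.4 points low under independent failures, and lower still with positive association. This rests on an assumed distant-failure rate, constant hazards, and a local-control figure from one small study.

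The shift is smaller than the standard error, the endpoint carries no test or threshold, and the primary survival endpoint is not touched. The reason to act is that the error runs one way relative to the death-censored estimate and is cheap to remove. If 10.7.2 governs and its results are recorded, mainly wording remains. The documents do not establish that recurrence data will be lost; they leave it open.

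**What to change.** 1. Reconcile 10.7.1 with 10.7.2, stating which follow-up applies after brain progression, for withdrawn patients and for those still on study. Settle the year-2 MRI interval against Section 10 at the same time.
2. State that, after the first brain progression, local recurrence, distant recurrence and salvage (type and date) continue to be recorded from the standard-of-care MRIs and visits that take place. This is the main remedy, because it does not depend on the two failures being independent.
3. In 13.5.1 and 13.5.2, censor patients without the event at the last brain MRI that assessed it. This fits Section 10's use of the most current MRI, but alone removes the bias only if the failures are independent.

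The cost is a short amendment, some added case report form entry and slightly shorter censored follow-up for recurrence. No visits or tests are added.
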